## b) Eating disorder psychopathology

- Number of OBEs (T0, T2) defined as for the primary endpoint
- Abstinence from objective binge eating (T1-T2) meaning `oepism1==0`
- Remission (T1-T2), (remission means `bedfull= bedlfrq = bedlimdu = nein`), partial remission (T1-T2), defined as change from `bedfull` to `bedlfrq` or `bedlimdu` – only those with `bedfull` at T0 will be included in the endpoint analysis of partial remission. All data will be included in descriptive statistics.
- Eating disorder psychopathology (EDE-Q) (T0-T2): the global score and the four subscale-scores (restraint, weight concern, shape concern, eating concern) will be used

## c) Neuropsychological outcomes (T0-T2)

- Cognitive flexibility: Trail Making Test (TMT-B), completion time in s, age- and sex-specific percentile rank
- Planning: Tower of London, number of correct responses, age- and sex-specific percentile rank
- Inhibition: Stop Signal, stop signal reaction time in ms, age- and sex-specific percentile rank; Go/NoGo, cued Go/NoGo, number of commission errors, age- and sex-specific percentile rank
- Decision making: Cards and Lottery Task, number of advantageous decisions
- Food-specific attention: Food-specific Dot-Probe, attentional bias score in ms
- Food-specific approach/avoidance: Food-specific Approach-Avoidance Task, difference score in ms per category (high-calorie, low-calorie, neutral-boring, neutral-pleasant)
- Food-specific inhibition: Food-specific Stop Signal Task, stop signal reaction time in ms

## d) Brain-activity-related outcomes

- fNIRS and fNIRS delayed treatment group, group-wise: Condition-(neurofeedback/transfer), block(first block/second block) and task-wise (regulation/mirror/rest) oxygenated, deoxygenated, and total haemoglobin values per session for the 2 individual fNIRS channels that were selected for training and for regions of interest.
- EEG group only (T0, T1): Eyes-closed (3min) and eyes-open (3min) resting-state and food-specific activity (90s) for theta, alpha, and beta band in  $\mu\text{V}$
- EEG group only: mean beta activity baseline and feedback in  $\mu\text{V}$  per session noted from TheraPrax device, amount of successful trials and % success in transfer trial per session

## e) Weight management-related behaviours (T0-T2)

- Self-efficacy (GSES): Sum score
- Impulsivity (BIS/BAS): Two scales: Behavioral Inhibition System (BIS) mean score and Behavioral Activity System (BAS) mean score
- Cognitive emotion regulation (CERQ): Sum scores for nine different conceptual scales: 1) Self-blame, 2) Acceptance, 3) Rumination, 4) Positive refocusing, 5) Planning, 6) Positive reappraisal, 7) Putting into perspective, 8) Catastrophizing and 9) Blaming others

- Emotion regulation (DERS): Global sum score. The six sub-scales will only be reported if there is a significant difference between randomization arms for the global score.
  - Food Craving Questionnaire-Trait (FCO-T-r): Sum score
- f) Mental health (T0-T2)
- Depressive symptoms (PHQ-D): Sum score
  - Anxiety disorder symptoms (PHQ-A): Sum score
  - Quality of life (SF-12): Physical and mental sum scores
- g) Physical health (T0-T2)
- Body mass index (BMI,  $\text{weight}/\text{height}^2 \cdot 10^4$ ), kg/m^2
  - Hip and waist circumference, cm

### 2.3 Further variables

Control variables at baseline (T0) are used to characterize the patients and may be relevant for outcomes, so that particular attention is warranted to ensure that random differences between the groups are not large.

- Vigilance: Perception and attention functions battery (WAFA), log-transformed mean reaction times in ms, measure of dispersion (variability in performance in intrinsic and phasic vigilance) in ms
- Intelligence: Raven's Coloured Progressive Matrices, number of correct responses, age- and sex-specific percentile rank
- Working memory: N-back task, number of correct responses, age- and sex-specific percentile rank

Variables that may be relevant for session-wise and overall neurofeedback outcomes assessed in each session:

- Helpfulness of the training: general (PRE31), related to eating behaviour (PRE32), to relax (PRE33), scale between 0-6
- Questions about strategies: Attempts to apply strategies in daily life during the past seven days (PRE41), success in applying the strategies used during training (PRE42), success in applying these strategies related to eating behaviour (PRE431) and to relax (PRE432)
- PHQ-15: sum score (variables PRE51 – PRE515)
- Strategies that were used for the session (POST21), reported in an exemplary fashion (Item 3c of the CRED-nf checklist)
- Success in regulating brain activity during the past session (POST22), scale between 0-6

### 2.3.1 Baseline characteristics

The following characteristics of the trial population at baseline will be calculated / reported descriptively by randomization arm.

- Sex (*sex*)
- Age (difference between *randodat* and *birth*, for the latter, only month and year are available and the first of the month will be used)
- Level of education as a binary variable (“A-levels” or not, *gradu==Abitur/Fachabitur*)
- BMI ( $\text{weight/height}^2 \cdot 10^4$ ), and according to the stratification variable
- Weight status (normal weight, overweight, obese, according to BMI)
- Participation in a weight-loss programme (stratification variable), yes/no
- Waist circumference (*waist*) stratified by sex, cm
- Hypertension (*dis1suf*), yes/no, and medication for hypertension (*dis1med*)
- Type II diabetes (*dis5suf*), yes/no, and medication for diabetes (*dis5med*)
- Previous comorbid psychiatric disorders (*PSYDIS*), yes/no
- Previous psychotherapeutic or psychiatric treatment (*THR*), yes/no
- Participation in previous self-help groups (*SPPGRP*), yes/no
- Lowest (*LOWGHT*) and highest adult weight (*HIWGHT*), kg
- Number of medically controlled (*MDCNTR*) and non-medically controlled (*NMDCNTR*) previous weight loss attempts, scale between never -  $\geq 5$  times
- Type of motivation to participate in the study (weight loss [*MNREAS*]/voluntary control of brain activity [*MNREAS1*])
- Motivation to change eating behaviour (*MTVN*), readiness to maintain changes in eating behaviour in the long-term (*WILL*), confidence in maintaining changes in eating behaviour in the long-term (*CONFI*), scale between 1-10

This list may be modified for the publication.

## 3 General analysis definitions

### 3.1 Analysis populations

Analysis of the primary and secondary outcomes are based on the full analysis set (FAS). Note that patients fulfilling the criterion for abstinence at T0 will not be included in the analysis for this endpoint. Further, the analysis of the primary outcome will be performed in the per-protocol set (PPS) to evaluate the treatment effect for patients with good protocol adherence, if FAS and PPS comprise a sufficiently different set of patients. Analysis of the fNIRS data will be performed in the fNIRS data set.

The FAS includes all randomized patients unless purely technical issues precluded the fNIRS measurements. In particular, three patients had to be replaced because of the aforementioned technical issues with fNIRS. Patients who could not complete the intervention due to the SARS-CoV-2 situation will be retained in the FAS if they completed at least 5 sessions and provided OBE data at T1. In control patients, those who could not attend T0WL due to SARS-CoV-2 will not be retained in the FAS.

The PPS includes all patients of the FAS without serious violations of the study protocol. The following protocol violations are classified as serious:

- Violation of at least one inclusion or exclusion criterion

- Treatment was not conducted as mandated, that is
  - Temporal delay of last attended treatment session by 4 weeks relative to the planned date, `exdat`, (based on the date of the first treatment session). Note that consideration of a maximum of two weeks' delay in each session as originally foreseen was not considered feasible.
  - Absence of more than 6 of the planned 12 treatment sessions (based on `meet`)
- Use of forbidden medication
- Psychological treatment during study participation (was not the case, otherwise it would be documented in the "comments")

The fNIRS/EEG data set includes all patients from the fNIRS/EEG group of the FAS who provided data for more than a single neurofeedback session. Participants with fewer sessions are excluded from the analyses, because the definition of neurofeedback *training* does not apply for these participants and there is no information on between-session variability.

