### 5.6.1 Discontinuation of the study intervention for individual patients

A patient may withdraw from the study at any time, at his or her own request, for any reason, specified or unspecified, and without penalty or loss of benefits to which the patient is otherwise entitled. Patients who have withdrawn from the study will not be allowed to re-enter later.

Furthermore, the responsible investigator has the right to discontinue the treatment of patients that experience one or more of the following incidents:

1. Adverse events (AE) or serious adverse events (SAE), particularly serious medical or psychological problems (e.g., cardiovascular disease, suicidal tendency, major depression) which do not allow any further treatment with the investigational intervention or which do not allow any further participation in the study because of impaired interpretability of the study results;
2. Reasons precluding attendance of scheduled visits;
3. Unacceptable benefit/risk ratio;
4. Lacking cooperation or compliance of the patient (i.e., intake of medication that is prohibited by the study protocol, intake of psychotropic or weight-affecting medications without indication, participation in psychotherapeutic interventions other than the study);
5. Refusal of the patient to continue participation.

The responsible investigator will make the decision about discontinuing treatment after contacting the coordinating investigator. Date of discontinuation, all recorded results at that time and, if known, the reasons for discontinuation are to be documented in the case report forms (CRFs). If possible, a final examination will be done. In any case, all patients will be followed up at each assessment time point after discontinuation, according to the intention-to-treat principle.

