## 7.5 Statistical methods

### 7.5.1 Analysis population

Analysis of the primary and secondary outcomes are based on the full analysis set (FAS). Further, the analysis of the primary outcome will be performed in the per-protocol set (PPS) to evaluate the treatment effect for patients with good protocol adherence, if FAS and PPS comprise a sufficiently different set of patients. For safety analysis, adverse events and SAEs will be analyzed descriptively.

The FAS includes all patients who were randomized. Every attempt will be made to acquire missing data for the primary outcome.

The PPS includes all patients of the FAS without serious violations against the study protocol. The following protocol violations will be classified as serious:

- At least one inclusion or exclusion criterion was not met.
- Treatment was not conducted as mandated, that is:
  - Temporal delay of at least one treatment session by 2 weeks of the planned date (based on the date of the first treatment session)

- Absence of more than 6 of the planned 12 treatment sessions
- Intake of forbidden medications
- Psychological treatment during study participation

Further serious protocol violations will be specified in the data analytic plan, if necessary.

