### 7.5.2 Planned methods for analysis

Primary analysis: The primary endpoint, the number of OBEs at post-treatment (t1) ~~and pre-treatment (t0)~~, will be investigated using ANCOVA with OBEs at t1 as the dependent variable, OBEs at t0 as a covariate as well as the stratification criteria. A closed-testing procedure will be used, meaning that the initial comparison will be between the two intervention groups combined and the waiting group and the three pair-wise tests (~~fNIRS vs. waiting group, EEG vs. waiting group and fNIRS vs. EEG~~) will be performed without adjustment if the global test is significant. The analysis will follow the intent-to-treat principle and will be based on the full analysis set. Every attempt will be made to acquire missing data. If data missing for the primary outcome can be expected to bias results in a meaningful way, multiple imputation will be performed. Further, the analysis of the primary outcome will be performed in the per-protocol set to evaluate the treatment effect for patients with good protocol adherence.

Secondary analyses: Recruitment and attrition rates will be described quantitatively and a qualitative analysis of the hurdles involved in recruitment and in maintaining patient commitment will be presented. Further secondary outcomes will be analyzed in an exploratory, descriptive manner, and will be evaluated presented with 95% CIs, as well as parametric or non-parametric tests, depending on the scale level and type of distribution of the observed variables. Multiple comparisons given three arms will be taken into account using e.g. Dunnett's test or Tukey's Honest Significant Differences and where all pair-wise comparisons will be made, independent of the result of a global test. Maintenance of treatment success over time will be evaluated. Predictors of treatment outcome will be identified using regression analyses.

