### 4.1 Primary endpoint

The primary endpoint, the number of OBEs at post-assessment or post-waiting, will be analysed using ANCOVA with OBEs as the dependent variable, OBEs at T0 as a covariate as well as the stratification criteria (`strabmi`, `stralsex`, `strawei`). The code for this test will have the structure

```
anova(lm(OBE_FU ~ OBE_T0 + STRABMI + STRASEX + STRAWEI + ARMS)).
```

The variables OBE\_FU and OBE\_T0 will be shifted by the mean of OBE at T0 so that the intercept in the model reflects change in time. A closed-testing procedure will be used, meaning

---

 The planned dates are as follows: session 1/2 (week 1), session 3/4 (week 2), session 5/6 (week 3), session 7/8 (week 4), session 9 (week 5), session 10 (week 6), session 11 (week 7), session 12 (week 8),

that the initial comparison will be between the two intervention groups combined and the waiting group and the three pair-wise tests (fNIRS vs. wait control group, EEG vs. wait control group and fNIRS vs. EEG group) will be performed without adjustment if the global test is significant. If the global test is not significant, estimates and confidence intervals will still be provided for the contrasts in OBE, but no formal statistical test will be carried out. Estimates will be taken from the linear model and a Wald confidence interval will be used. Moreover, secondarily, the analogous analysis with effect size will be performed.

Missing data will be treated with multiple imputation using the R package “mice” (van Buuren and Groothuis-Oudshoorn 2011). The imputation variables will include the answer to the question “In how many of the situations in which you ate too did you feel you had lost control of your eating behaviour” (pre72). Sex, BMI and the stratification variable participation in a weight-loss programme will also be used. Fifty imputations will be performed.

To test the robustness of the results, the primary analysis will be repeated without imputation and pessimistic and optimistic scenarios will be considered.

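### The SAP's full analysis set drops some randomised patients for post-randomisation reasons that differ by arm, so the primary analysis is not the intention-to-treat analysis the protocol promises

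*SAP*

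**What the plan says.** Protocol section 7.5.1 states: "The FAS includes all patients who were randomized". Section 7.5.2 adds for the primary endpoint: "The analysis will follow the intent-to-treat principle and will be based on the full analysis set". Section 5.6.1 supports this by requiring, after treatment is stopped, that "all patients will be followed up at each assessment time point after discontinuation, according to the intention-to-treat principle".

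SAP section 3.1 bases the primary and secondary analyses on a set with the same name but different membership:

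- Rule 1, technical: "The FAS includes all randomized patients unless purely technical issues precluded the fNIRS measurements". It reports that "three patients had to be replaced because of the aforementioned technical issues with fNIRS".
- Rule 2, patients who could not finish the intervention because of SARS-CoV-2: they "will be retained in the FAS if they completed at least 5 sessions and provided OBE data at T1". By implication, the others are removed.
- Rule 3, waiting-list controls: "those who could not attend T0WL due to SARS-CoV-2 will not be retained in the FAS". Under SAP section 2.1, T0WL is the visit that supplies the control arm's primary endpoint.

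SAP section 4.1 then says: "Missing data will be treated with multiple imputation using the R package", with fifty imputations. The robustness checks are a repeat without imputation and pessimistic and optimistic scenarios. No analysis of all randomised patients is named.

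The SAP marks two other changes from the protocol as changes: the 28-day binge-eating window (section 2.1) and the treatment-delay rule for the per-protocol set (section 3.1). It does not mark the change to the FAS.

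**The concern.** Randomisation takes place at the baseline visit, before any treatment (Protocol sections 5.3 and 5.4). All three rules therefore act on later events, and rules 2 and 3 set different conditions in different arms. Once membership of the analysis set depends on such events, the comparison no longer has the protection of randomisation. The set also governs the pooled neurofeedback versus waiting-list test, which decides whether the three pairwise tests are performed at all.

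Two features make this more than a matter of naming. Rule 2 can delete a patient whose primary outcome was measured, because too few sessions were attended; exposure conditions of that kind belong in the per-protocol set. Rules 2 and 3 also delete some patients because the outcome is missing, which is the situation the imputation in section 4.1 exists to handle.

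**Working it through.** **Who is kept and who is removed under SAP 3.1 and 4.1**

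| Patient | Treatment in the plan |
|---|---|
| Active arm, stopped early for a reason other than SARS-CoV-2, any number of sessions | Kept; a missing outcome is imputed |
| Active arm, completed the intervention, missed T1 because of SARS-CoV-2 | Caught by no rule: kept and imputed |
| Active arm, cut short by SARS-CoV-2, at least 5 sessions, T1 observed | Kept |
| Active arm, cut short by SARS-CoV-2, at least 5 sessions, T1 missing | Removed |
| Active arm, cut short by SARS-CoV-2, fewer than 5 sessions, T1 observed | Removed, although the outcome is known |
| Waiting list, missed T0WL because of SARS-CoV-2 | Removed |
| fNIRS technically impossible | Removed (three replaced) |

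The second and sixth rows show the inconsistency: the same cause of a missing primary outcome leads to imputation in one arm and deletion in the other. The session condition in rule 2 cannot apply to the waiting list before T0WL, because those patients have had no sessions by then.

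The per-protocol set excludes absence from more than 6 of 12 sessions, so it requires at least 12 − 6 = 6 attended. The FAS condition for patients cut short by SARS-CoV-2 is 5. Among those with T1 data, the two sets differ on session count only for a patient with exactly 5 sessions.

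**Possible size**

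The plan gives no figure for this effect. From the documents: 26 patients per arm, so 52 active against 26 controls, and a planned effect of 0.55 SD for the pooled comparison (Protocol 7.4.4), used here only as a yardstick. The only exclusion count given is three. Assumed: k = 3, 5 or 8 of the 52 active patients are removed, none from the waiting list, and the outcomes of those removed are δ = 0.5 or 1.0 SD worse than those of the patients kept.

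The mean of all randomised patients equals the mean of those kept plus (k/n) × δ, so the shift from exclusion is (k/n) × δ.

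| k of 52 | δ = 0.5 | δ = 1.0 |
|---|---|---|
| 3 | 0.03 SD | 0.06 SD |
| 5 | 0.05 SD | 0.10 SD |
| 8 | 0.08 SD | 0.15 SD |

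As a share of 0.55 SD, the extremes are 0.029/0.55 = 5% and 0.154/0.55 = 28%. If all k were in the fNIRS arm (n = 26), the shift in the fNIRS contrasts would double, to between 3/26 × 0.5 = 0.06 SD and 8/26 × 1.0 = 0.31 SD. With δ = 0 every entry is zero.

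A simulation of the two-sample t-test (20,000 runs, 52 versus 26, no true difference among all randomised, two-sided 5%) gave rejection rates of 5.3% to 5.8% at δ = 0.5. At δ = 1.0 they were 5.6%, 6.7% and 9.4% for k = 3, 5 and 8. The all-randomised analysis stayed between 4.3% and 5.1% throughout.

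**What imputation can recover**

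A second simulation (52 versus 26, baseline correlation 0.5, k = 3, 5 or 8 active patients with no outcome and 1 SD worse) compared exclusion with imputation from arm and baseline. The bias was 0.057, 0.096 and 0.162 SD under both, agreeing with (k/n) × δ within simulation error. Imputation under missing-at-random therefore restores the population but does not by itself remove this bias. The gain comes from observed T1/T0WL values now discarded and from in-session information: Protocol section 5.4 lists binge-eating episodes among the weekly treatment-phase assessments.

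**The case against.** The strongest reply is that this is a modified intention-to-treat set, stated openly, in a feasibility study disrupted by a pandemic. Equipment failure and closures may have nothing to do with how a patient would have fared, and the number of sessions reached when the pandemic struck may reflect entry date more than motivation. That stands as a limit on size: zero bias is possible. It does not make the analysis intention-to-treat.

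The documents do not support several stronger readings that a reader might draw:

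- That poor attenders in general are removed, which would favour neurofeedback. The 5-session condition covers only patients cut short by SARS-CoV-2; other early dropouts stay in and are imputed. Rule 3 also removes some controls, so the net direction is not known.
- That every patient missing the outcome because of SARS-CoV-2 is deleted. An active patient who completed treatment is not.
- That the three replaced patients came from the fNIRS arm. Their arm is not stated. Brain-activity measures, with Go/NoGo as an example, are listed at baseline for all arms (Protocol 5.3), and a Go/NoGo task was part of the fNIRS localiser (SAP 6.11.1).
- That the feasibility results are inflated. The CONSORT flowchart in SAP section 4 covers all randomised patients, including treatment and assessment completion, and section 2.2 reports attrition with SARS-CoV-2 dropout taken into account. What remains is an ambiguity: section 3.1 ties secondary outcomes to the reduced FAS, and section 2.2 names no other denominator.

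**Conclusion.** The point holds on the text. The protocol and the SAP define the same named set differently, the SAP does not mark the change, and the primary analysis as now specified is not intention-to-treat. The clearest fault is the deletion of an observed primary outcome because of low exposure. The second is the inconsistent handling of outcomes lost to SARS-CoV-2.

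The size and direction of any bias cannot be established, because the SARS-CoV-2 exclusions are not counted and no arm is given for the three replaced patients. The range of about 0.03 to 0.15 SD in the pooled test rests wholly on the assumptions of 3 to 8 of 52 excluded, all from the active arms, and 0.5 to 1.0 SD worse. It should be read as what could happen, not as an estimate. The change is still worth making, since this set underlies the confirmatory test.

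**What to change.** 1. Define the FAS as all randomised patients in the arm assigned, including the three who were replaced.
2. Use every observed T1 or T0WL binge-eating count. Impute missing ones whatever the reason, adding in-session data to the imputation model where they exist.
3. Apply the pessimistic and optimistic scenarios to this full set, because missing-at-random imputation alone will not remove bias for patients with no outcome data.
4. Keep the present definition as a sensitivity analysis labelled modified FAS, with exclusions tabulated by arm and reason, and record it as a departure from Protocol section 7.5.1.
5. State that attrition and assessment completion use all randomised patients as the denominator.

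The cost is a change of SAP wording, one extra run, and slightly wider intervals from the additional imputed values.

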	
Control intervention (1): 12 sessions (60 min) over 8 weeks of electroencephalography (EEG) neurofeedback (high beta training)
 
Control (2): 8 weeks without treatment, after which 12 sessions (60 min) over 8 weeks of fNIRS neurofeedback will be offered (delayed treatment control condition)

Primary outcome:	The number of objective binge-eating episodes (OBEs) over the past 14 days at post-treatment (t1), derived from the Eating Disorder Examination, will be compared between groups, correcting for the baseline value
Secondary outcome:	
 
- Feasibility including recruitment, attrition, assessment completion, patients' program evaluation
 
- Eating disorder psychopathology
 
- Executive functioning
 
- Weight management behavior
 
- Mental and physical health
 

Biometry:	
Efficacy / test accuracy: The comparison between the groups with respect to binge eating episodes directly after treatment.
 
Safety: Report of type and frequency of adverse events.
 
Secondary endpoints: Descriptive analyses, effect sizes, presented with 95% confidence intervals, parametric or non-parametric tests, regression analyses.

Trial duration:	
Duration of intervention per patient: 8 weeks
 
Follow-up per patient: 6 months
 
First patient in to last patient out (months): 25 months
 
Duration of the entire trial (months): 30 months
 
Recruitment period (months): 17 months

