## 5.4 Description of the study procedure

Following the baseline visit including randomization (see 5.3), patients will receive active treatment or control (fNIRS neurofeedback/EEG neurofeedback) or delayed treatment which involves a period of 8 weeks without treatment. If a patient was randomized into the delayed treatment condition, the following variables will be assessed prior to the treatment 8 weeks after randomization:

Time point	Variable
Only delayed treatment  Before start of therapy Week 8 (+ max. 2 weeks)	
 
Anamnesis
 
Comorbidities
 
Medication intake
 
Anthropometry
 
Sociodemographics
 
Eating disorder psychopathology e.g., Eating Disorder Examination (EDE)
 
General psychopathology e.g., Patient Health Questionnaire (PHQ)
 
Neuropsychological and brain activity-related measures e.g., Go/NoGo task
 
Behavioral measures e.g., Bogus taste test
 
Visual analogue scales (VAS): expectations, motivation
 

During treatment, all patients will be assessed weekly (i.e. at each treatment session), including the following variables:

Time point	Variable
During treatment, weekly Active treatments: Weeks 1-7 Delayed treatment: Weeks 9-15	
 
Brain activity-related outcomes e.g., EEG frequency band power
 
Visual analogue scales (VAS): state craving, liking, sense of control, hunger, satiety, and mood
 
Objective binge-eating episodes
 
(Serious) adverse events
 

The following variables will be assessed at the end of treatment, 8 (fNIRS neurofeedback and active control treatments) or 16 (delayed treatment control condition) weeks after randomization.

Time point	Variable

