## 2 Endpoints and further variables

### 2.1 Primary endpoint

The number of objective binge-eating episodes (OBEs) over the past 28 days at post-assessment (T1, **visit\_label=T1** for the intervention groups) or after the waiting period (**visit\_label=T0WL** for the waitlist control group; Item 6a of the CRED-nf checklist). OBEs are derived from the well-established Eating Disorder Examination interview (**oepism1**) and will be compared between groups, correcting for the baseline value (**visit\_label=T0**). The trial protocol stipulated that the number of OBEs over the past 14 days would be analysed. Based on the standard EDE instrument and the accepted endpoint, the value over the past 28 days will be used (Item 6a of the CRED-nf checklist).

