### 2.2 Secondary endpoints (Item 6a of the CRED-nf checklist)

Unless otherwise indicated, the scores from questionnaires are calculated using the “qscorer” package from [name] (see appendix for code). Comparisons between all three groups are foreseen at T0 (baseline) and T1/T0WL. After T0WL, the WL control group received an fNIRS intervention. Hence, T2 can only be used to estimate changes within a group and between the two intervention groups.

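### The per-protocol session and medication criteria have no limit by arm or time, so read literally they can drop waitlist patients for conduct after their primary endpoint at T0WL

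*SAP*

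**What the plan says.** SAP 3.1 defines the set without naming arms: "The PPS includes all patients of the FAS without serious violations of the study protocol". The violations listed as serious include "Absence of more than 6 of the planned 12 treatment sessions" and "Temporal delay of last attended treatment session by 4 weeks relative to the planned date", the latter "based on the date of the first treatment session". Use of forbidden medication is listed too, with no time window. Protocol 7.5.1 has the same absence criterion and its own delay and medication criteria, also without an arm or time limit.

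The primary endpoint is measured at T1 in the fNIRS and EEG arms "or after the waiting period" in the waitlist arm, that is, at T0WL (SAP 2.1). Treatment of the waitlist arm comes later. The Protocol synopsis describes this arm as "8 weeks without treatment, after which 12 sessions (60 min) over 8 weeks of fNIRS neurofeedback will be offered". Protocol 5.4 times the assessments during treatment as "Delayed treatment: Weeks 9-15". SAP 2.2 confirms the order: "After T0WL, the WL control group received an fNIRS intervention".

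The PPS analysis is supportive. Under SAP 3.1 and Protocol 7.5.1 it is run only if the PPS differs enough from the FAS. The primary analysis uses the FAS.

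**The concern.** In the fNIRS and EEG arms, attendance precedes the endpoint, so a session criterion describes the treatment whose effect is being measured. In the waitlist arm the same criterion describes something that happens after the endpoint has been recorded. A waitlist patient can respect the waiting period in full, attend T0WL, and then lose a place in the PPS by declining or missing later sessions.

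Control patients would then be selected on post-outcome behaviour. If that behaviour is related to the number of objective binge-eating episodes (OBEs) at T0WL, the waitlist mean in the PPS is no longer that of the patients who complied with the control condition. A forbidden-medication violation after the primary assessment raises the same problem in every arm. At stake is the PPS analysis, which is meant to show the effect under good adherence, and possibly the decision whether to run it, since that depends on how far the PPS differs from the FAS.

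**Working it through.** **Step 1. Order of events.**

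- fNIRS and EEG: randomisation, 12 sessions over 8 weeks, primary endpoint at T1 (week 8), follow-up.
- Waitlist: randomisation, 8 weeks untreated, primary endpoint at T0WL (week 8), then 12 sessions offered, end of therapy (week 16), follow-up.

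No waitlist session falls before the waitlist endpoint.

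**Step 2. What the criteria do to the waitlist arm under each reading.**

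1. Applied to the delayed sessions. Both criteria can be computed: 12 sessions are planned, and the delay is anchored on the patient's own first session. Waitlist patients are then selected on conduct after T0WL.
2. Applied only to sessions up to T0WL. Every waitlist patient has 0 of 12 sessions, so 12 absences, which exceeds 6. The control arm is empty. A time limit alone therefore does not repair the session criteria.
3. Applied to fNIRS and EEG only. This is workable but is not written.

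**Step 3. Size of the shift under reading 1.** The plan gives no figure for this. As a yardstick I use the planning values in Protocol 7.4.4: effect 0.55 SD, 42 pooled intervention and 21 waitlist patients. (With these values a two-sided t-test has 52.6% power, not the stated 80%. That is a separate matter, and nothing here depends on it.) The share removed and its relation to outcome are not in the documents and are assumptions.

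By simple arithmetic, the kept mean minus the full mean is p × (kept mean − removed mean), where p is the share removed:

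- 0.10 × 0.3 SD = 0.03 SD, 5% of 0.55
- 0.20 × 0.5 SD = 0.10 SD, 18% of 0.55
- 0.30 × 0.8 SD = 0.24 SD, 44% of 0.55

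As a check with a selection model, let q be the share of waitlist patients removed, ρ the correlation between later attendance and OBEs at T0WL, and z_q the q-quantile of the standard normal. The shift of the waitlist mean is ρ·φ(z_q)/(1 − q):

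- any q, ρ = 0: shift 0
- q = 5%, ρ = ±0.3: 0.3 × 0.103/0.95 = ±0.033 SD
- q = 20% (about 4 of 21), ρ = ±0.3: 0.3 × 0.280/0.80 = ±0.105 SD
- q = 20%, ρ = ±0.5: 0.5 × 0.280/0.80 = ±0.175 SD
- q = 30%, ρ = ±0.5: 0.5 × 0.348/0.70 = about ±0.25 SD, or 45% of 0.55

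Positive ρ means that patients with more OBEs attend more. Removal then raises the waitlist mean and favours neurofeedback. Negative ρ does the opposite.

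**Step 4. Effect on the test.** Simulation with 8,000 runs per case, 42 v 21 patients, two-sided t-test at 5% without covariates. The same share is removed from the active arms, unrelated to outcome.

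| q | ρ | Type I error | Mean estimate when truth is 0.55 |
|---|---|---|---|
| 20% | 0 | 4.7% | 0.55 |
| 20% | +0.3 | 6.5% | 0.65 |
| 20% | +0.5 | 8.5% | 0.72 |
| 20% | −0.3 | 6.1% | 0.44 |
| 30% | +0.5 | 12.0% | 0.80 |

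With the session criteria limited to the active arms, the type I error is 4.9% to 5.2% and the mean estimate about 0.55 in every case. This calculation omits the baseline adjustment in the planned ANCOVA, so ρ is best read as the association left after that adjustment.

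**The case against.** The strongest reply is that the SAP never says the session criteria apply to the waitlist arm, and that its context suggests otherwise. The session bullets sit under treatment not delivered as mandated, whereas waitlist treatment is only offered. The FAS paragraph just above judges control patients by attendance at T0WL, and the attrition count in SAP 2.2 covers the intervention groups only. Protocol 12.1 also has violations discussed with the biometrician before analysis, which gives an occasion to settle the matter.

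This stands in part: a reading limited to the active arms is plausible. It is not what the section says, though. SAP 3.1 names arms where it means to, in the FAS rule for control patients and in the fNIRS/EEG data sets, and does not do so for these bullets. SAP 2.2 also plans session-wise fNIRS values for the delayed treatment group, so those sessions are part of the planned data. Nothing elsewhere resolves the question, and it should not be left to a choice made once results are known.

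A reader might go further and infer that the plan will remove waitlist patients and so inflate the neurofeedback effect, on the argument that patients who improved unaided have less reason to complete delayed treatment. The documents do not support this. No text links later attendance to OBEs at T0WL. Patients who stayed unwell or became discouraged might equally stay away, which would shrink the effect. Attendance selection in the active arms could add to the shift or offset it.

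Nor does the psychological-treatment criterion add to the problem in practice. It also lacks a cut-off at the primary assessment, but the SAP records that no such treatment occurred.

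**Conclusion.** The point holds as a defect of wording with a possible, unquantified consequence. The session-absence, session-delay and forbidden-medication criteria have no arm or time limit. Applied as written, the two session criteria select waitlist patients on conduct after their endpoint, and the medication criterion can do so in any arm.

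Bias follows only if that conduct is related to OBEs at the primary assessment or to their causes. Over assumed removal of 5% to 30% of waitlist patients and correlations from −0.5 to +0.5, the shift runs from 0 to about 0.25 SD in either direction. The upper end needs both the largest removal and the strongest correlation, and a 30% removal exceeds the 20% drop-out that the protocol assumes.

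The consequence is confined to a supportive, conditional analysis. The FAS primary analysis and the closed-testing procedure do not depend on it. It is worth correcting because the remedy is short and the current text permits three different per-protocol sets.

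**What to change.** Add to SAP 3.1: the session-absence and session-delay criteria apply to the fNIRS and EEG arms only; all other post-randomisation PPS criteria count only violations up to the patient's primary assessment, which is T1 for fNIRS and EEG and T0WL for the waitlist. Both parts are needed, because a time limit without the arm limit would empty the waitlist arm. Fix the wording before the PPS is formed.

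The change needs no new data and alters no trial procedure. It has one small downside: only the active arms are then selected on adherence and are compared with a waitlist arm not selected in that way. That asymmetry should be stated when the PPS result is interpreted.
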